**Model Checking & Diagnostics**

- The fit of the regression models will be examined using “Q-Q” plots of the standardized residuals. Interpretation of these plots will be aided by the addition of simulated envelopes as proposed by Atkinson (Atkinson, 1985).
- The Gelman-Rubin R estimate will be calculated for all parameters in the model and the rate ratios vs. placebo for each danirixin dose.
- Autocorrelation plots will be visually inspected to assess degree of autocorrelation (should decline rapidly and show no oscillation patterns).

**Model Results Presentation**

- Model estimated median exacerbation/event rate and associated 90% CrI for each treatment group
- Median rate ratio and associated 90% CrI, percent reduction in annual exacerbation/event rate and associated 90% CI for each danirixin dose vs. placebo
- The probability that the true exacerbation rate ratio is less than 1, 0.9 and 0.8 for each danirixin dose will be presented
- A figure of the rate ratios and associated 90% CrIs for each danirixin dose vs. placebo

**Summary Results Presentation**

For HCRU exacerbations:

- Number and percent of participants reporting an exacerbation (mild, moderate, severe and moderate/severe), number and percent of participants with each number of moderate/severe exacerbations (0, 1,  $\geq 2$ ), the total number of exacerbations per treatment and annual raw exacerbation rate (as defined in Section 14.6.3). This table will be repeated for HCRU exacerbations that were treated with Antibiotics and will include the number and percentage of participants who were receiving ICS treatment at the time of the exacerbation.
- For each moderate/severe exacerbation, the outcome, severity, duration, whether the exacerbation led to hospitalization, systemic/oral corticosteroids being taken, antibiotics being taken, or emergency room visit.

For EXACT events:

- Number and percent of participants reporting an EXACT-defined event, number and percent of

participants with each number of EXACT-defined events (0, 1,  $\geq 2$ ), the number of EXACT-defined events and annual raw event rate (as defined in Section 14.6.3) will be summarized for all events and for recovered, censored and persistent worsening events separately for each treatment group. The duration and severity (indicated by the maximum observed value and duration) will be reported for all events.

### **Sensitivity and Supportive Analyses**

- At the strategic interim a supportive analysis of HCRU exacerbations will be conducted to estimate the effect of the randomized treatment. The population used will be the ITT (according to randomized treatment). A 'treatment policy' strategy will be used to account for the intercurrent event of occurrence of a protocol deviation considered to impact efficacy during the treatment period (see Appendix 1). All on-treatment exacerbations up the time of treatment discontinuation will be used in the analysis, regardless of any protocol deviation. An 'as treated' strategy will be used to account for the intercurrent event of treatment discontinuation – no exacerbations will be recorded after treatment discontinuation/study withdrawal.

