Concomitant medication review	X	X	X	X	X	X	X	X	X	X	X	X	X

Procedure	Pre-Screening ^a (Visit 0)	Screening ^a (Visit 1)	Study Visits									Early Withdrawal	Follow Up (up to 28 days post last dose)
			2	3	4	5	6	7	8	9	10		
Study Day			-7	1	14	28	56	84	112	140	168		
Assessment Window	-30 d		±0d	+ 3d	±3d	±3d	±3d	±3d	±3d	±3d	±3d		
Clinical Outcomes Assessments													
COPD Exacerbations			←=====→									X	X
EXACT-PRO ^j			←=====→										
Rescue Medication Use ^k			←=====→										
SGRQ-C				X				X			X	X	
COPD Assessment Test				X				X			X	X	
PROactive Questionnaire ^l				X				X			X		
Physical Activity Monitor ^l			X					X			X		
Participant Global Impression of COPD Severity			X										
Participant Impression of Change in COPD Severity					X	X	X	X	X	X	X	X	
Participant Global Impression of Activity Limitation			X										

Procedure	Pre-Screening ^a (Visit 0)	Screening ^a (Visit 1)	Study Visits									Early Withdrawal	Follow Up (up to 28 days post last dose)
			2	3	4	5	6	7	8	9	10		
Study Day			-7	1	14	28	56	84	112	140	168		
Assessment Window	-30 d		±0d	+ 3d	±3d	±3d	±3d	±3d	±3d	±3d	±3d		
Participant Impression of Change in Activity Limitation					X	X	X	X	X	X	X	X	
Genetic, Pharmacokinetic and Biomarker Blood Collections													
Blood sample for Genetics				X									
Blood sample for pharmacokinetics (PK) ^m				X			X	X			X		
Blood sample for Fibrinogen				X				X			X	X	
Blood sample for CRP				X				X			X	X	
Blood Sample for Exploratory Biomarkers				X				X			X	X	

Procedure	Pre-Screening ^a (Visit 0)	Screening ^a (Visit 1)	Study Visits									Early Withdrawal	Follow Up (up to 28 days post last dose)
			2	3	4	5	6	7	8	9	10		
Study Day			-7	1	14	28	56	84	112	140	168		
Assessment Window	-30 d		±0d	+ 3d	±3d	±3d	±3d	±3d	±3d	±3d	±3d		

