10.5.1.3. HCRU Exacerbations

The number of events associated with HCRU-defined exacerbations will be analyzed using generalised linear models assuming a negative binomial distribution for the underlying exacerbation rate with a log link and an offset to account for the length of time in study for each participant. The exacerbation rates for the danirixin and placebo groups, along with the ratio in exacerbation rates danirixin/placebo, will be estimated and corresponding 95% credible intervals will be produced.

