10.5.1.4. Time to First HCRU Exacerbation

Time to first HCRU exacerbation will be defined from the date of randomization. Participants without an exacerbation and participants who withdraw from the study prior to any observed exacerbations will be censored at the time of last contact. Survival will be summarized by treatment groups through Kaplan-Meier curves. Treatment arms will be compared using a stratified log-rank test. Time to first severe HCRU exacerbation will be analysed in a similar manner.

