
discontinue study treatment and continue participant in the study for any protocol specified follow up assessments
 
MONITORING:
 
For bilirubin or INR criteria:
 
 Repeat liver chemistries (include ALT, AST, alkaline phosphatase, bilirubin) and perform liver event follow up assessments within 24 hrs Monitor participants twice weekly until liver chemistries resolve, stabilize or return to within baseline A specialist or hepatology consultation is recommended 
For All other criteria:
 
 Repeat liver chemistries (include ALT, AST, alkaline phosphatase, bilirubin) and perform liver event follow up assessments within 24-72 hrs Monitor participants weekly until liver chemistries resolve, stabilize or return to within baseline 	
liver injury, or hypersensitivity, on the AE report form
 
 Record use of concomitant medications on the concomitant medications report form including acetaminophen, herbal remedies, other over the counter medications. Record alcohol use on the liver event alcohol intake case report form (CRF) page 
For bilirubin or INR criteria:
 
 Anti-nuclear antibody, anti-smooth muscle antibody, Type 1 anti-liver kidney microsomal antibodies, and quantitative total immunoglobulin G (IgG) or gamma globulins. Serum acetaminophen adduct high performance liquid chromatography (HPLC) assay (quantifies potential acetaminophen contribution to liver injury in participants with definite or likely acetaminophen use in the preceding week [James, 2009]). Liver imaging (ultrasound, magnetic resonance, or computerised tomography) and /or liver biopsy to evaluate liver disease; complete Liver Imaging and/or Liver Biopsy CRF pages.
---	---

- Serum bilirubin fractionation should be performed if testing is available. If serum bilirubin fractionation is not immediately available, discontinue study treatment for that participant if ALT \geq 3xULN **and** bilirubin \geq 2xULN.. Additionally, if serum bilirubin fractionation testing is unavailable, **record presence of detectable urinary bilirubin on dipstick**, indicating direct bilirubin elevations and suggesting liver injury.

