## 7. EFFICACY ANALYSES

Details of the planned displays including the population to be used for each display and which displays are produced for the strategic interim are presented in [Appendix 11](#). Additional details are provided below.

For this study, no data were scheduled to be collected after discontinuation of study treatment, therefore accounting for non-recorded missing data following study withdrawal is addressed by the strategy for the intercurrent event of treatment discontinuation.

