
 
The time to first on-treatment Moderate/Severe HCRU exacerbation will be calculated as exacerbation onset date of first on-treatment moderate or severe on-treatment exacerbation – date of start of treatment +1
 
Participants will be represented from their treatment start date to their first on-treatment moderate or severe exacerbation or date of censoring.
 
For the strategic interim analysis, participants that have not experienced an on-treatment exacerbation are censored at the earliest of (treatment stop date + 3, date of death, or the interim cut-off date, 1AUG2018).
 
For the final analysis, participants that have not experienced an on-treatment exacerbation are censored at the earliest of (treatment stop date + 3, date of death, date of exclusion from the per protocol population (if analysis is in Per Protocol population))
 

Raw Annual Rate

 
Raw annual rate is the event rate per 1000 participant-years, calculated as the number of events x 1000, divided by the total duration at risk (minimum(treatment stop date + 1, date of death, date of exclusion from the per protocol population (if analysis is in Per Protocol population)) – treatment start date + 1).
 

Offset Variable

 
For analyses of exacerbation rate, the offset variable will be defined as the logarithm of the ((minimum (date of end of study treatment + 3, date of death, date of exclusion from the per protocol population (if analysis is in Per Protocol population)) – date of start of treatment + 1)/365.25)
 

EXACT Events
General

 
The daily EXACT-PRO scores will be computed according to the EXACT-PRO user manual (Evidera, 2016a) and used to identify EXACT-defined events, including the frequency, duration and severity of the events.
 
Events will be categorized as recovered, censored, or persistent worsening (according to the manual).
 

Time to First Event

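### The SAP says no exacerbations are recorded after treatment stops, although the Schedule of Activities collects them to follow-up, and it moves the exacerbation analyses from time in study to on-treatment + 3 days without declaring the change

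*SAP*

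**What the plan says.** **Collection.** The protocol's Schedule of Activities (Table 1) has a row for "COPD Exacerbations" that runs across the study visits and is marked again at Early Withdrawal and in the column headed "Follow Up (up to 28 days post last dose"). SAP Appendix 2 reproduces the same row. For participants who meet a liver stopping rule, Protocol Appendix 7 tells sites to "discontinue study treatment and continue participant in the study for any protocol specified follow up assessments".

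**Protocol analysis.** Section 10.5.1.3 fits a negative binomial model with "an offset to account for the length of time in study for each participant". Section 10.5.1.4 says that "participants who withdraw from the study prior to any observed exacerbations will be censored at the time of last contact", and handles time to first severe exacerbation in a similar way.

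**SAP premise.** Section 7 says that "no data were scheduled to be collected after discontinuation of study treatment". Section 7.2.1.5.1, for the ITT supportive analysis at the strategic interim, says that "no exacerbations will be recorded after treatment discontinuation/study withdrawal".

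**SAP analysis.** Sections 7.2.1.5.1 and 7.2.2.5.1 restrict the rate and time-to-first endpoints to on-treatment events. Section 14.4.1.3 counts an event as on-treatment if its onset is no later than stop date + 3 days, and classes later onsets as post-treatment. Section 14.6.3 ends the rate offset at end of treatment + 3 days. For time to first it says that "participants that have not experienced an on-treatment exacerbation are censored at the earliest of (treatment stop date + 3, date of death" or, at the final analysis in the per-protocol population, at the date of exclusion from that population.

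**Declaration.** Section 2.1 presents SAP Table 1 as the list of changes from the protocol's analysis plan. It has a row for the interval level of the exacerbation rates (95% to 90%) but none for the observation window.

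**The concern.** There are two faults. First, the SAP rests its handling of treatment discontinuation on the absence of later data, whereas exacerbations are scheduled to be collected after stopping and the SAP has a category for them. Second, the time at risk for the exacerbation rate, a key secondary endpoint, and for the time-to-first endpoints has changed from time in study to time on treatment + 3 days without appearing where such changes are declared.

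At stake is a limited set of recorded events. A separate moderate or severe episode that begins after stop + 3 is left out of the rate, the time to first exacerbation and the time to first severe exacerbation. SAP sections 7.2.1.4 and 7.2.2.4 aim at the effect had participants stayed on treatment. Ending follow-up at stop + 3 serves that aim only if, given the model covariates, stopping is unrelated to later exacerbation risk. For participants who stop because they are getting worse that is doubtful, and such stopping may differ by arm. Without an analysis over the longer window, a reader of the report cannot see whether the choice matters.

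**Working it through.** The documents give no expected exacerbation rate, event count or power for these endpoints, so there is no planned figure to reproduce. The check compares definitions and then does time-at-risk arithmetic.

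**Definitions compared**

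| Item | Protocol | SAP |
|---|---|---|
| Events counted | Recorded HCRU exacerbations | Onset up to stop + 3 |
| Rate offset | Time in study | To end of treatment + 3 |
| Time-to-first censoring | Last contact | Stop + 3 |
| Collection after stopping | Early Withdrawal and follow-up visits | Stated as none, yet a post-treatment phase is defined |

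In the SAP's list of displays (Appendix 11), every final exacerbation table and figure is either titled on-treatment or built on the on-treatment models. Post-treatment exacerbations can appear only in Listing 48.

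**Inputs.** About 600 randomized, about 10% dropout and 168 days of treatment (Protocol 5.1 and 5.2). Follow-up at most 28 days after last dose (Schedule of Activities). SAP margin 3 days. Check: 600 × (1 − 0.10) = 540, the protocol's completer figure, leaving about 60 early stoppers.

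**Days excluded per participant.** 28 − 3 = 25 at most (stop + 4 to stop + 28). If follow-up falls on day 14 it is 11 days; on day 7, 4 days.

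**Early stoppers**
- 60 × 25 / 365.25 = 4.1 participant-years at most (1.8 at 11 days, 0.7 at 4 days).
- On-treatment time, assuming early stoppers average 84 days: (540 × 168 + 60 × 84) / 365.25 = 262 participant-years.
- Share: 4.1 / 262 = 1.6%.
- Events at an assumed 0.5 to 1.5 per year: 4.1 × 0.5 = 2.1 to 4.1 × 1.5 = 6.2. Spread evenly over six arms, that is about 0.3 to 1 per arm.

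**All participants**
- A completer contributes 168 + 3 = 171 days under the SAP and up to 168 + 28 = 196 under the protocol. The difference is 25 / 196 = 12.8% of time in study.
- 600 × 25 / 365.25 = 41.1 participant-years at most (18.1 at 11 days, 6.6 at 4 days). About nine-tenths of this is completers' follow-up after planned treatment ended.

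**Which event is excluded.** Protocol 9.1.2 dates an exacerbation from the first day of worsening symptoms, and SAP 14.4.1.3 classifies by onset date, treating a missing onset date as on-treatment. Suppose a participant stops on Day 70 because of worsening and is admitted on Day 75 for the same episode. Onset is normally no later than Day 70, so the event counts as on-treatment. Only a new episode starting after Day 73 is left out.

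**The case against.** The strongest reply is that on-treatment analysis is an openly stated estimand, suited to a phase IIb dose-ranging study. Protocol 6.1 equates 60 hours with about 6 half-lives, so 3 days (72 hours) covers about 7, and later events occur essentially off drug. The protocol also leaves further analysis detail to the RAP. All of this stands as a defence of the choice. It does not cover the incorrect premise or the undeclared change, because the protocol states its offset and censoring rules explicitly.

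The statement that nothing is recorded after discontinuation sits in an ITT analysis confined to the strategic interim, which has already been run. That is correct, and rewording it changes no final result. But the section 7 premise is general, and the stop + 3 rule in 14.6.3 governs the final analysis too.

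Several stronger readings are not supported:

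- A reader might infer that someone who stops because of worsening is censored event-free. Onset dating and the 3-day margin normally keep that episode. Protocol 8.1.4 and 9.1.2 also allow treatment to be paused for an exacerbation, so a pause need not be the final stop date.
- A reader might infer that SAP 7.2 promises a full treatment-policy effect and fails to deliver it. Section 7.2.1.5.1 applies treatment policy to protocol deviations and an as-treated strategy to discontinuation. That is an explicit mixture, loosely summarized in 7.2.
- A reader might assume a high rate just after stopping, say 4 per year, and reach about 16 lost events (4.1 × 4). That combines a rate the documents do not give with a full 28-day follow-up for every dropout, including those lost to follow-up.
- A reader might say the events are discarded. They stay in Listing 48 and are only left out of the analyses.

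**Conclusion.** The point holds as a mismatch between protocol and SAP with a small, unquantified risk of bias. The SAP's statements that nothing is scheduled or recorded after stopping are contradicted by the Schedule of Activities and by its own post-treatment phase. The move to on-treatment + 3 days departs from the protocol's stated analyses, is missing from SAP Table 1, and leaves later episodes out of every final efficacy table and model.

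Among early stoppers, where censoring could be informative, the excluded time is at most about 4.1 participant-years, 1.6% of on-treatment time, or roughly 2 to 6 events. This rests on 60 early stoppers, full 28-day follow-up for each, a mean of 84 days on treatment and an assumed 0.5 to 1.5 events per year. The total gap between the definitions, up to about 41 participant-years, is mostly completers' off-drug follow-up. Nothing in the documents shows that excluded events would fall unevenly across arms. Time to first severe exacerbation is the most exposed, since severe events are likely to be fewest. Correction and a sensitivity analysis are warranted; abandoning the on-treatment analysis is not.

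**What to change.** - Correct SAP section 7 and section 7.2.1.5.1 to say that exacerbations are collected at Early Withdrawal and follow-up, and that the on-treatment analysis leaves out onsets after stop + 3 by choice.
- Add a row to SAP Table 1 for the change from time in study and last-contact censoring to on-treatment + 3 days, with the rationale.
- Keep the on-treatment analysis. At the final analysis add, as a sensitivity analysis for the rate and both time-to-first HCRU endpoints, what the protocol states: all recorded moderate/severe exacerbations (severe only for that endpoint), offset equal to time in study, and censoring at last contact. Use the mITT population, as the protocol does, because exclusion 10 in SAP Appendix 1 removes per-protocol data from the stop date for anyone off study medication for more than 14 days.
- If a version capped at Day 168 is also wanted, to keep completers' off-drug follow-up out, label it as additional. The protocol has no such cap.
- While editing 14.6.3, reconcile the raw annual rate, whose time at risk ends at stop + 1, with the stop + 3 event window. For a completer, 171 / 169 − 1 = 1.2% overstatement.

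The cost is SAP wording and three reruns of existing models with a later end date, on data already collected. The downside is that some off-drug time enters the sensitivity analysis, so it should be shown beside the on-treatment result and not in its place.

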## **7.2.2. Time to First HCRU Exacerbation and EXACT Event**

### **7.2.2.1. Endpoint**

Time to first moderate/severe HCRU exacerbation as defined in Section 14.6.3.

Time to first severe HCRU exacerbation as defined in Section 14.6.3.

Time to first EXACT event as defined in Section 14.6.3.

### **7.2.2.2. Summary Measure**

Hazard ratio (also expressed as percentage risk reduction) for each danirixin dose vs. placebo)

### **7.2.2.3. Population of Interest**

PP population

### **7.2.2.4. Strategy for Intercurrent (Post-Randomization) Events**

The intercurrent events of interest are occurrence of a protocol deviation considered to impact efficacy during the treatment period (see Appendix 1) and treatment discontinuation. An 'as treated' strategy will be used to account for these events to estimate the effect if participants had not deviated from the protocol and remained on treatment. Only first exacerbations/EXACT events prior to the occurrence of a protocol deviation considered to impact efficacy will be used in the analysis.

## 7.2.2.5. Statistical Analyses / Methods

### 7.2.2.5.1. Statistical Methodology Specification

Endpoint / Variables

 
• Time to first On-treatment moderate/severe HCRU exacerbation
 
• Time to first On-treatment severe HCRU exacerbation
 
• Time to first On-treatment EXACT event
 

Model Specification

 
• Bayesian proportional hazards model
 
• Terms in the model: 
 
○ Response: time to first on-treatment, moderate/severe HCRU exacerbation or EXACT event
 
○ Categorical: treatment group, gender, exacerbation history (<math>\leq 1</math>, <math>\geq 2</math> moderate/severe), smoking status (screening), country
 
○ Continuous: post-bronchodilator % predicted FEV1 (Screening)
 
○ Non-informative priors will be used for all modelling parameters. Wherever possible conjugate priors will be utilised.
 
○ All the terms in the model will follow a normal distribution with a mean of 0 and a SD of 100
 
 
 
• The 'exact' method will be used for handling ties. If the analysis will not run using the 'exact' method, then the 'Efron' method for handling ties will be used instead.
 
• Three chains will be used to calculate the gelman-rubin R statistic: 
 
○ Chain 1: The starting value for all covariates in the model will be the MLE, except dispersion which will be 0.1.
 
○ Chain 2: The starting value for all covariates in the model will be 130% of the MLE, except for dispersion which will be 0.2.
 
○ Chain 3: The starting value for all covariates in the model will be 70% of the MLE, except for dispersion which will be 0.4.
 
 
 
• The seeds used to for the three chains were generated using the ranuni function in SAS and are listed in Section 14.5.2.
 
• Burn-in 2000, thin 5, and 10,000 MCMC samples will be generated for 2000 retained samples
 
• Kaplan-Meier survivor functions will be obtained for each treatment group using PROC LIFETEST with a TIME statement.
 

Model Checking & Diagnostics

 
• The proportional hazards assumption will be examined by obtaining the Kaplan-Meier estimates of the survival function <math>S(t)</math> over time separately for each treatment group. In addition, the <math>\ln \{-\ln[S(t)]\}</math> plot will be produced.
 

Model Results Presentation

 
• Hazard ratio and the percent reduction in risk for each danirixin dose compared with placebo with associated 90% CrI.
 
• The probability of having an event, 90% CrI and first quartile and median time to event for each treatment group will be presented.
 
• The probability that the true hazard ratio is less than 1 for each danirixin dose will be presented.
 

- Kaplan-Meier curves showing the probability of having an event over time for each treatment group separately plotted on the same figure

